Data Management and Statistical Analyses. Parents will input their data into a RedCap database accessible via the internet. Missing data for continuous variables that cannot be recovered from parents will be imputed using either subscale or total scale mean score substitutions (e.g., HFS-PYC, PIP, CES-D). Again, covariates for Hypotheses 2a-b and 3a-b will be parents' depressive symptoms (DS), and child age (AGE).

Hypotheses.

Hypothesis 1: RED CHiP will be feasible and acceptable to families of young children with T1DM.

Hypothesis 2a and b: Parents who receive RED ChiP will have a reduction in fear of hypoglycemia (HFS-PYC) and parenting stress (PIP) as compared to the wait-list group (*Hyp 2a*) and pre-RED ChiP measures (*Hyp 2b*).

Hypothesis 3: Children whose parents receive RED ChiP will experience an improvement in mean glycemic levels (MDBG & HbA1c) and variability (ADRR & LBG1) as compared to the wait-list group (*Hyp 3a*) and pre-RED ChiP measures (*Hyp 3b*).

Power analysis. This is a pilot and feasibility study with the purpose of generating data to support a full, randomized controlled trial. Power analysis of a test of the difference between pre- and post-HFS-PYC with a 10% decline in survey scores (i.e., from $M=78.6 \pm 18.4^{17}$ to $M=71$) yielded a power of 84%, while a 15% decline in PIP-F scores (i.e., from a $M=107.2 \pm 32.6^{27}$ to $M=91$) yielded a power of 92% when $n=40$, $\alpha=0.05$ for both tests. Repeated measures ANCOVA (RM-ANCOVA via GLM) yielded a power of 92% and 82%, respectively, for 10% declines in parents' HFS-PYC and PIP-F scores. When using RM-ANCOVA and assuming a 10% decline in children's HbA1c, tests yielded 95% power when $n=40$ and $\alpha=0.05$ ($M=8.8 \pm 1.5\%$ to 8.0%). Assuming an attrition rate of 20%, we will need to recruit 48 parents (24 per group) to ensure we have ≥ 40 parents with post-treatment data. This sample size is also sufficient to estimate effect sizes for the study outcomes.

Data Analysis. We will first run descriptive statistics and statistical distributions for all measured variables at baseline (B), weeks 15-16 (w15-16), and weeks 32-33 (w32-33). We will conduct sensitivity analyses for all primary outcomes to evaluate any effects due to attrition. We will also use an intent-to-treat analysis strategy, wherein we will use an imputation model to examine participant data even if they are lost to attrition.

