	Average Daily Risk Range (ADRR)	A measure of risk of glycemic variability; ⁵¹ scores are calculated based on a minimum of 14-days of self-monitoring blood glucose (SMBG) data; scores >40 suggest a high risk for variability; has been used previously in young children; ³⁵ our pilot data show a correlation between children's ADRR scores and percent of low blood glucose values ($r=0.93$, $p=0.03$)
	Low Blood Glucose Index (LBGI)	A measure of risk for a low blood glucose level; ⁴⁵ based on a normalized transformation of SMBG to remove bias due to the natural asymmetry of blood glucose (greater range of hyper versus hypoglycemic levels); LBGI is based on a minimum of 14-days of data; sensitive to hypoglycemic events only; our pilot data show a correlation between children's LBGI and percent of low blood glucose values ($r=0.88$, $p<0.001$)
SECONDARY MEASURES:	Feasibility (Quantitative)	Feasibility of RED ChiP will be based on attendance to group sessions $\geq 70\%$ and attrition $\leq 25\%$
	Acceptability (Quantitative)	Acceptability of RED ChiP will be based on our Treatment Satisfaction Questionnaire, a 16-item measure; the Treatment Satisfaction Questionnaire will use a 5-point Likert scale to assess perceived acceptability of the RED ChiP content and structure (mean score ≥ 65 , range: 16-80)
COVARIATES:	Demographic & Medical History	Family/child characteristics; medical history; T1DM events; we will collect this during the baseline assessment; child age will be used as a covariate
	Center for Epidemiologic Studies-Depression Scale (CES-D)	20-item self-report; ⁴⁷ reliable in parents of children with T1DM; ²⁹ superior to Beck Depression Inventory in identifying depressive symptoms in T1DM; ^{46,48-49} Total Score will be used as a covariate; higher values suggesting greater frequency of depressive symptoms

Note. Please see Appendix A for sample questions from each measure.

Hypotheses 2a and b: We will score outcome measures as continuous variables with within-group standardized effect sizes (in SD units) and within-group changes for FH (HFS-PYC) and parenting stress (PIP-F and PIP-D) calculated based on parents' B, w15-16, and w32-33 scores. To test for between-group differences on parents' FH and stress at B, w15-16, and w32-33, we will use both repeated measures ANCOVA (RM-ANCOVA) and a 2x2 factorial (condition x time) MANCOVA. We will also use these to test for *within-group x time* differences. Our covariates will be AGE and DS.

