Hypotheses 3a and b: We will calculate within-group standardized effect sizes (in SD units) and within-group changes for children's glycemic levels and variability based on children's B, w15-16, and w32-33 values. As in Hypothesis 2, we will employ General Linear Models (GLMs) such as RM-ANCOVA and a 2x2 factorial (condition x time) MANCOVA to test for between-group differences on children's glycemic levels (MDBG & HbA1c) and variability (ADRR & LBGI) at B, w15-16, and w32-33 and for *within-group x time* differences. Our covariates will be AGE and DS.

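### The stated RM-ANCOVA power of 92%, 82% and 95% names no contrast and does not hold for the 20-versus-20 comparison with the wait-list

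*Combined protocol and SAP*

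**What the plan says.** The Power analysis paragraph of the combined protocol and SAP gives two sets of figures at alpha 0.05.

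- **Pre/post test, n=40:** 84% for a 10% decline in HFS-PYC (78.6, SD 18.4, to 71) and 92% for a 15% decline in PIP-F (107.2, SD 32.6, to 91).
- **RM-ANCOVA:** "Repeated measures ANCOVA (RM-ANCOVA via GLM) yielded a power of 92% and 82%, respectively, for 10% declines" in HFS-PYC and PIP-F, and 95% for HbA1c (8.8, SD 1.5, to 8.0). n=40 is printed for HbA1c and implied for the other two.

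The 40 are both arms together. The paragraph recruits 24 per group "to ensure we have ≥ 40 parents with post-treatment data", and the Procedure section targets at least 20 completers per group. It adds: "This sample size is also sufficient to estimate effect sizes for the study outcomes".

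Hyp 2a and 3a predict improvement "as compared to the wait-list group"; Hyp 2b and 3b predict improvement on pre-treatment values. The analysis text for Hypotheses 2a and b reads: "To test for between-group differences on parents' FH and stress at B, w15-16, and w32-33, we will use both repeated measures ANCOVA (RM-ANCOVA" together with a 2x2 MANCOVA, and then: "We will also use these to test for *within-group x time* differences". For Hypotheses 3a and b it names models "such as RM-ANCOVA and a 2x2 factorial (condition x time) MANCOVA to test for between-group differences on" the glycemic outcomes. So RM-ANCOVA serves both kinds of question.

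**The concern.** A power figure describes one contrast. Here the same model name covers a comparison of 20 families with 20 others and a comparison of families with themselves, and the power paragraph does not say which was calculated. Every effect in it is worded as a decline from a starting mean, yet a reader who looks up the test for Hyp 2a/3a finds RM-ANCOVA and may take 82-95% as its power.

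The wait-list arm crosses over after 14 weeks (Wait-list Control section), so weeks 15-16 is the only time point at which treated and untreated families are compared. That comparison carries Hyp 2a/3a on outcomes that the plan lists as primary. If its power is far below 82-95%, a non-significant result could be misread as evidence of no effect when the full trial is planned, and supporting that trial is the pilot's stated purpose.

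**Working it through.** **Inputs from the Power analysis paragraph**

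| Outcome | Decline | SD | Decline in SD units | Stated RM-ANCOVA power |
|---|---|---|---|---|
| HFS-PYC | 7.6 (printed means) or 7.86 (exact 10%) | 18.4 | 0.413 or 0.427 | 92% |
| PIP-F | 10.72 (10% of 107.2) | 32.6 | 0.329 | 82% |
| HbA1c | 0.8 (printed means) or 0.88 (exact 10%) | 1.5 | 0.533 or 0.587 | 95% |

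Alpha is 0.05 and sidedness is not stated. **Assumptions, not in the documents:** baseline-to-post rho 0.5 to 0.7; no change in the wait-list arm.

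**Step 1: the plan's own figures.** For a paired test on 40 families, the noncentrality is decline × √40 / (SD × √(2(1−rho))), with 39 df.

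- The pre/post figures are recovered. One-sided at rho 0.5 gives 84.4% (HFS-PYC, 7.86) and 92.2-92.5% (PIP-F, 15% decline). Two-sided at rho 0.6 gives 83.8% and 92.5-92.9%.
- The RM-ANCOVA figures cannot be reproduced from the printed inputs, because rho and the contrast are missing. Read as a two-time-point change in all 40, they need rho of about 0.62-0.71 (HFS-PYC), 0.68-0.75 (PIP-F) and 0.39-0.58 (HbA1c), across one- and two-sided tests and both versions of the decline.

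**Step 2: 20 versus 20 at weeks 15-16.** For ANCOVA adjusted for baseline, child age and depressive symptoms:

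- residual SD = SD × √(1−rho²)
- standard error = residual SD × √(2/20)
- df = 40 − 5 = 35

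Example, HFS-PYC at rho 0.6: residual SD = 18.4 × 0.8 = 14.72; standard error = 14.72 × 0.3162 = 4.655; noncentrality = 7.86/4.655 = 1.689; two-sided power 37.6%. With a decline of 7.6 the noncentrality is 1.633 and power is 35.5%.

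| Outcome | Stated | Two-sided, rho 0.5 / 0.6 / 0.7 | One-sided, rho 0.5 to 0.7 |
|---|---|---|---|
| HFS-PYC, 7.6 | 92% | 31.1 / 35.5 / 42.8% | 43.4-55.9% |
| HFS-PYC, 7.86 | 92% | 32.9 / 37.6 / 45.2% | 45.4-58.3% |
| PIP-F, 10.72 | 82% | 21.5 / 24.4 / 29.4% | 32.0-41.4% |
| HbA1c, 0.8 | 95% | 47.4 / 53.6 / 63.2% | 60.4-74.9% |
| HbA1c, 0.88 | 95% | 54.9 / 61.6 / 71.4% | 67.6-81.7% |

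**Step 3: rho needed for the stated powers at 20 versus 20** (one- and two-sided): 0.90-0.93 (HFS-PYC), 0.92-0.94 (PIP-F), 0.83-0.89 (HbA1c).

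**Step 4: sensitivity over rho 0.5 to 0.7.**

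- All 48 analysed (24 versus 24), two-sided: 36-53%, 25-35%, and 55-72% or 63-79%. One-sided: 49-65%, 36-47%, and 68-82% or 75-88%.
- Change scores in place of baseline adjustment, 20 versus 20, two-sided: 17-65% across outcomes.
- Three-period model, 20 versus 20, two-sided, with the effect persisting so that the arms are level again at weeks 32-33. With equal correlations the residual variance factor is 1 − 2rho²/(1+rho), which is 0.667 at rho 0.5 and 0.424 at 0.7, against 0.75 and 0.51 for ANCOVA. Power is 34-52%, 24-34%, and 52-71% or 60-79%.

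**Step 5: what 20 versus 20 can deliver** (two-sided)

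| rho | Difference detectable at 80% power | HFS-PYC points | PIP-F points | HbA1c percentage points | 95% CI half-width |
|---|---|---|---|---|---|
| 0.5 | 0.79 SD | 14.5 | 25.7 | 1.18 | 0.556 SD |
| 0.6 | 0.73 SD | 13.4 | 23.8 | 1.09 | 0.514 SD |
| 0.7 | 0.65 SD | 12.0 | 21.2 | 0.98 | 0.458 SD |

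The effects assumed in the plan are 7.6-7.9, 10.7 and 0.8-0.88.

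**The case against.** **The figures may be sound for another contrast.** This stands. As within-person change in all 40 they need only ordinary correlations, and the effects are worded as declines from baseline. No printed figure is shown to be miscalculated. But the within-person reading is an inference too: RM-ANCOVA is named for the between-group tests, and the sponsor may have meant Hyp 2a/3a. A reader might conclude that the figures can only be within-person, and the documents do not settle that.

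**The three outcomes need different correlations.** A reader might take this as a sign of error. It is not: two questionnaires and a laboratory value need not share one correlation.

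**ANCOVA at weeks 15-16 is not the planned model.** True: the plan names RM-ANCOVA over three time points. A three-period model with a persisting effect gives somewhat more power, but still less than stated over this range of rho.

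**The shortfall rests on assumed values.** Also true. Higher rho narrows it: at rho 0.8, two-sided, ANCOVA power is 56-59% (HFS-PYC), 39% (PIP-F) and 78% or 85% (HbA1c). One-sided testing helps as well, and the pre/post figures would fit one-sided testing at rho 0.5. The HbA1c upper value of 71% needs a fall of 0.88; with the printed means it is 63%.

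**It is a pilot.** This lowers the consequence, and the plan itself says that the sample serves to estimate effect sizes. It does not remove the point, because the plan states power and states Hyp 2a/3a as tested hypotheses on primary outcomes.

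**Conclusion.** The point holds as an unlabelled power statement that the controlled comparison cannot meet. At rho 0.5 to 0.7 with an unchanged wait-list arm, two-sided 20-versus-20 power at weeks 15-16 runs from about 21% to 71% across the three outcomes, against the stated 82% to 95%. The chance of missing the assumed effects is then about 29-79%, where the stated figures imply 5-18%. One-sided testing (32-82% power), analysis of all 48 families and the three-period model each leave every outcome below its stated figure over that range of rho.

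A reader might go further and infer that the plan claims 82-95% for the wait-list comparison, or that its calculation is wrong. The documents support neither: they do not say which contrast was calculated. That the figures fail for 20 versus 20 at ordinary correlations is well supported; what they were meant to describe is unknown. The point should be fixed, and it does not put the study's feasibility aims in doubt.

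**What to change.** 1. State the contrast, assumed correlation, sidedness and number of time points behind the 92%, 82% and 95%. If they are within-person, say so and say that they do not apply to Hyp 2a/3a. If they were meant for Hyp 2a/3a, replace them.
2. For Hyp 2a/3a, state the 20-versus-20 power at weeks 15-16 with its assumptions, or the difference detectable at 80% power. At an assumed rho of 0.6, two-sided, that is about 0.73 SD: roughly 13 HFS-PYC points, 24 PIP-F points and 1.1 HbA1c percentage points (0.65-0.79 SD over rho 0.7 to 0.5).
3. Report the wait-list comparison as a between-group estimate with a 95% confidence interval. The expected half-width at rho 0.6 is about 0.51 SD: roughly 9 HFS-PYC points, 17 PIP-F points and 0.8 HbA1c percentage points. The Data Analysis section now specifies only within-group effect sizes, so this adds what the estimation aim needs.

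The cost is a rewritten power paragraph and one or two sentences in the analysis section, with no extra families, visits or data. The downside is a less favourable stated power for the controlled comparison.

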Procedure. The study will use a randomized wait-list controlled design. The parent (mother or father) primarily involved in their child’s daily T1DM management will be invited to participate with their child. We will plan to recruit 24 families to each of the immediate treatment and wait-list control groups (we will target at least 20 families per group to complete the study; 20% attrition rate). A member of the research team will identify families eligible to participate. Parents will undergo randomization after they provide written informed consent. We will stratify parents based on their child’s gender and conduct random assignment to the two groups using blocks of four. We intend to recruit three family cohorts each consisting of 16 families (8, immediate treatment, 8 wait-list). We will instruct parents randomized to the wait-list control group to follow their physician’s recommendations for their child’s T1DM. Then, after the 14 week wait-list control period, we will invite parents in the control group to participate in RED CHiP. We will instruct parents randomized to the immediate treatment group to follow their physician’s recommendations for their child’s T1DM. In addition, they will receive 14 weeks of RED CHiP. Parents randomized to the immediate treatment group will also complete a follow up assessment, corresponding with the time when parents in the wait-list control group have finished the RED CHiP program (see Figure 2). Because we plan to use a mixed-method approach to evaluate the feasibility and acceptability of RED CHiP, we will also randomly sample 5 parents from both the immediate treatment and wait-list control groups (n=10 total) to complete a semi-structured qualitative interview. Parents will complete the interview at the time of their last assessment visit (e.g., followup, for parents in the immediate treatment group; post-treatment for parents in the wait-list control group). Parents will be able to complete all of the surveys online either with their own computer or an iPad 2 loaned to them by the study. A research assistant will work with parents to complete the online surveys, download children’s glucometers and insulin pump, and collect a finger stick blood sample to measure children’s Hemoglobin A1c (HbA1c) at each time point.

Figure 2. Intervention Timeline

[figure not shown]

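### Recruiting 48 at the plan's own 20% attrition yields about 38 completers (19 per group), not the 40 or more it says are ensured

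*Combined protocol and SAP*

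**What the plan says.** The Power analysis paragraph links recruitment, attrition and completers in one sentence: "Assuming an attrition rate of 20%, we will need to recruit 48 parents (24 per group) to ensure we have ≥ 40 parents". The 40 are parents from whom data are available after treatment. The Procedure section gives the same figures per arm: "We will plan to recruit 24 families to each of the immediate treatment and wait-list control groups", followed by "we will target at least 20 families per group to complete the study; 20% attrition rate".

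The power statements rest on the 40. The pre/post test on the HFS-PYC is described "with a 10% decline in survey scores (i.e., from $M=78.6 \pm 18.4^{17}$ to $M=71$) yielded a power of 84" percent, and the one on the PIP-F "a 15% decline in PIP-F scores (i.e., from a $M=107.2 \pm 32.6^{27}$ to $M=91$) yielded a power of 92" percent, both at n = 40 and α = 0.05. The HbA1c repeated-measures ANCOVA figure is also stated at n = 40. The repeated-measures ANCOVA figures for the two surveys (92% and 82%) carry no n of their own.

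**The concern.** A recruitment target adjusted for attrition should return the required number of completers once the attrition rate is applied to it. This one does not. The same 20% appears beside both numbers in two sections, so the contradiction is visible from the plan's own figures.

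At stake is the basis of the sample-size justification. If the trial runs exactly as assumed, it will on average miss the n at which power was quoted. The stated purpose of this pilot is to support a full randomised trial, so the same inflation method could carry into that trial's sample size, where a larger enrolment would make the shortfall larger in absolute terms.

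**Working it through.** **Inputs** (Power analysis and Procedure): recruited N = 48, 24 per group; attrition d = 0.20; required completers 40, 20 per group.

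**1. Reproducing the plan's figure.** The plan shows no inflation formula. Two forms were tried.

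| Form | Total | Per group |
|---|---|---|
| n × (1 + d) | 40 × 1.2 = 48 | 20 × 1.2 = 24 |
| n / (1 − d) | 40 / 0.80 = 50 | 20 / 0.80 = 25 |

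The first form matches the plan exactly. Only the second leaves n after a fraction d is lost.

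**2. Forward check.** Completers = N × (1 − d):
- total: 48 × 0.80 = 38.4
- per group: 24 × 0.80 = 19.2

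**3. Break-even attrition.** 1 − 40/48 = 8/48 = 16.7%. The per-group target also requires no more than 4 losses in either arm (24 − 4 = 20).

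**4. Chance of reaching the target.** Assume each family drops out independently with probability 0.20.
- P(at least 40 of 48 complete) = P(losses ≤ 8), Binomial(48, 0.20) = 0.358.
- P(at least 20 of 24 complete in one group) = P(losses ≤ 4), Binomial(24, 0.20) = 0.460. For both groups, 0.460² = 0.21.
- For comparison, with 50 recruited: P(losses ≤ 10), Binomial(50, 0.20) = 0.58.

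**5. Effect on power.** The plan gives neither the sidedness of the test nor the SD of change, so both must be assumed. The calculation is a paired t-test (noncentral t) at α = 0.05, with standardised effect = decline / SD of change.

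| Assumptions | n = 40 | n = 38 |
|---|---|---|
| HFS-PYC, exact 10% decline (7.86), SD 18.4, one-sided | 84.4% | 82.6% |
| HFS-PYC, printed means (78.6 − 71 = 7.6), SD 18.4, one-sided | 82.2% | 80.4% |
| HFS-PYC, 7.86, SD 18.4, two-sided | 75.0% | 72.7% |
| HFS-PYC, 7.86, two-sided, pre/post correlation 0.6 | 83.8% | 81.8% |
| PIP-F, exact 15% decline (16.08), SD 32.6, one-sided | 92.2% | 91.0% |
| PIP-F, printed means (107.2 − 91 = 16.2), SD 32.6, one-sided | 92.5% | 91.3% |
| PIP-F, 16.2, two-sided, pre/post correlation 0.6 | 92.9% | 91.5% |

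The first three rows and the one-sided PIP-F rows take the SD of change as equal to the baseline SD. With exact percentage declines, the one-sided version reproduces the plan's 84% and 92%. The level of power depends on the assumptions, but the loss from 40 to 38 stays at roughly 1 to 2 points throughout.

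**The case against.** The arithmetic cannot be disputed. The case on the other side concerns its weight and some details.

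- **It is a small shortfall in a pilot.** Two recruits, 1.6 expected completers and 1 to 2 points of power change no hypothesis, test or threshold. This stands, and it limits the finding to a wrong statement.
- **The analysis is not restricted to completers.** The Data Analysis section plans an intent-to-treat analysis with imputation, and attrition sensitivity analyses. That is true, but the sentence promises parents who have post-treatment data, and imputed parents do not. Imputation does not restore the lost information either.
- **The cause is inferred.** No formula is shown, and 48 is also three cohorts of 16 families, as set out in Procedure. This stands: adding attrition to the target is the likely explanation because the match is exact, but it is not documented. The shortfall does not depend on it.
- **Recruiting 50 would not ensure 40 either.** Correct: the chance is 58% under independent dropout. Independence is itself an assumption, since treatment is delivered in group cohorts.
- **Procedure only sets a target.** It is worded less strongly than the Power analysis, but the numbers it pairs are inconsistent in the same way.

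**Conclusion.** The concern holds. The sample-size statement is wrong as written: at 20% attrition, 48 recruited gives 38.4 expected completers (19.2 per group) against a stated minimum of 40 (20 per group). This part needs no assumption beyond the plan's own figures.

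The 36% chance of reaching 40 rests on independent dropout at exactly 20%. The power loss of about 1 to 2 points rests on the assumed sidedness and SD of change. The result does not show a materially underpowered trial; it shows that a guarantee in the sample-size justification is not met in expectation and would be missed more often than not.

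**What to change.** Keep 48 and correct the text in both Power analysis and Procedure, in one of two ways:

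1. State that 20% attrition leaves about 38 completers (19 per group), and recompute every power figure at n = 38, giving the sidedness, the SD of change and the n for each.
2. State that the target of 40 completers allows for at most 16.7% attrition (8 families, no more than 4 in either group).

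The first is cleaner. The second would put another attrition figure beside the feasibility limits, which already differ: Hypothesis 1 gives 20 without a unit, and Table 3 gives 25%. Read as 20%, the first limit permits 9 losses of 48 and leaves 39. The second permits 12 and leaves 36. Under either limit the trial could be called feasible while missing 40, so these limits should be reconciled in the same edit.

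The cost is wording changes in two places, a recalculation, and about 1 to 2 points less stated power. No extra enrolment is required. If the sponsor prefers to keep 40 expected completers at 20% attrition, recruitment would have to rise to 50 (25 per group), and the text should then say expected, not ensured.

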
Orientation. A trained research assistant will conduct orientation visits following randomization for families in the immediate treatment group and the wait-list period for families in the wait-list control group. These visits will include training on how to use the iPad and *Real Presence m500 app*.

Accelerometer. During RED CHiP, children will wear an accelerometer (Actigraph GT3X) for at least 5 days to measure their typical daily physical activity (PA). In young children, the link between glycemic response and PA remains unclear. Accelerometer data will provide an accurate measure of children's PA, since research shows that parents often underreport their child's engagement in unstructured PA.⁴¹ Children's total daily PA (total movement counts/total measurement time in minutes) will be calculated as well as a diagram of their typical daily PA patterns. We will use these data to educate parents regarding the relationship between their child's activity patterns and blood glucose levels. We expect that giving parents specific strategies for insulin dosing and carbohydrate intake in the context of their child's typical PA routine will improve parents' T1DM management and children's glycemic control.

Wait-list Control. After randomization, families assigned to the wait-list control condition will receive a copy of the clinics' standard flow sheet for the treatment of hypoglycemia. Families will cross over to the treatment arm at the end of the 14-week wait-list period.

Outcome Measures. Primary outcome measures will be: parents' FH, parenting stress, children's glycemic levels (measured using mean daily blood glucose levels and HbA1c), and children's glycemic variability (measured using the average daily risk range and the low blood glucose index). Secondary outcome measures will be the Feasibility and Acceptability of RED CHiP. Covariates for these pilot analyses will be parents' depressive symptoms and child age (see Table 3). If more than one parent participates in RED CHiP, we will use the data from the parent who self-identifies as the most responsible for their child's T1DM management in the study analyses. If parents indicate equal responsibility, we will collect data from both parents for each time point and we will average both parents' data for the analyses.

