Hypothesis 1: (Quantitative data): We will assume feasibility if families' mean group session attendance is $\geq 70\%$ and participant attrition is ≤ 20 . We will assume acceptability if parents' mean scores on the Treatment Satisfaction Questionnaire are ≥ 65 . **(Qualitative data):** We will use Framework Matrix Analysis (FMA) initially. FMA is an efficient approach to qualitative data analysis where data are analyzed using themes derived *a priori* instead of *de novo*.⁵² *A priori* themes will be based upon the interview agenda (viz., strengths, weaknesses, ways to improve RED ChiP and overall study feasibility). Thus, use of FMA will allow refinement of RED ChiP within the limited timeframe of the R21 mechanism. We will apply a grounded theory approach to analyze transcripts upon completion of all interviews. This more comprehensive approach will allow for identification of *de novo* themes, which will be integrated into RED ChiP protocols and submitted for publication.^{53, 54}

Table 3. Planned Assessment Measures

	Measure	Description
PRIMARY MEASURES:	Hypoglycemia Fear Survey (HFS-PYC)	26-item parent-report of fear of hypoglycemia; reliable and psychometrically sound for use in young children with T1DM; ^{17,26} we will use the Total Score, measuring both worry and behavior related to hypoglycemia prevention
	Pediatric Inventory for Parents (PIP)	42-item measure of parenting stress; reliable and psychometrically sound for use in parents of young children with T1DM; ^{27,42-43} we will use the Frequency (PIP-P) and Difficulty (PIP-D) scores
	Mean daily glucose (MDBG)	14-day glucometer downloads; we will use data for the 2 weeks preceding each assessment point
	Hemoglobin A1c (HbA1c)	Proxy measure of average glucose control; will be measured by automated high performance liquid chromatography (reference range: 4.0-6.0%, Tosoh 2.2, Tosoh Corporation, San Francisco, CA); measurement method is reliable to DCCT standards; ⁴⁴ all HbA1c will be measured by a central laboratory at CMH; CMH has recorded excellent reliability between preserved fingerstick and fresh venous blood samples ($r=0.98$)

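### The feasibility rule for Hypothesis 1 carries two different attrition limits, 20 in the analysis text and 25% in Table 3

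*Combined protocol and SAP*

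**What the plan says.** The rule appears twice in the combined protocol and SAP.

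- **Hypothesis 1 (Quantitative data), under Data Analysis:** feasibility is assumed if mean group-session attendance is at least 70% "and participant attrition is ≤ 20". No unit is printed after the 20.
- **Table 3, Secondary measures, Feasibility (Quantitative):** "Feasibility of RED ChiP will be based on attendance to group sessions $\geq 70\%$ and attrition $\leq 25", followed by a percent sign.

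Three other places bear on how the rule should be read.

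- **Procedure**, on 24 families recruited per group: "we will target at least 20 families per group to complete the study; 20% attrition rate".
- **Power analysis:** "Assuming an attrition rate of 20%, we will need to recruit 48 parents (24 per group"), the aim being "to ensure we have ≥ 40 parents with post-treatment data".
- **Status of the outcome:** Outcome Measures says "Secondary outcome measures will be the Feasibility and Acceptability of RED CHiP", while Power analysis says "This is a pilot and feasibility study with the purpose of generating data to support a full, randomized controlled trial".

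**The concern.** The attendance limit is identical in the two places, so they are two statements of one rule, and the attrition limit differs between them. No text gives precedence to either, or says that they apply to different groups or times. A pre-set threshold is useful only if there is one of it. With two on file, a result that falls between them can be reported as feasible or not feasible, and the choice can be made after the attrition figure is known.

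A related gap is that neither statement gives the denominator (all 48 families, or each group of 24) or the time point (weeks 15-16 or weeks 32-33). The time point matters because the wait-list group begins the programme only after its 14-week wait, so losses counted at the two assessments are not the same thing.

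**Working it through.** **Inputs.** Limits of 20 (Hypothesis 1 text) and 25% (Table 3); 48 families, 24 per group (Procedure, Power analysis); planning attrition of 20% (same sections); at least 40 completers (Power analysis).

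**The plan's own figure.** 40 × (1 + 0.20) = 48 reproduces the recruitment number. Dividing instead, 40 / (1 − 0.20) = 50.

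**Can the two limits be reconciled?** The percent sign may have been lost when the PDF was read, so nothing here rests on its absence. Read as a percentage, the conflict is 20% against 25%. Read as a count, 20 / 48 = 41.7%, which also disagrees with 25%. Neither reading removes the conflict. The 20% planning rate makes the percentage reading the natural one.

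**Losses allowed,** as the whole number at or below limit × n:

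| Denominator | Limit 20% | Limit 25% | Counts with opposite verdicts |
|---|---|---|---|
| 48 | 9.6, so 9 | 12 | 10, 11, 12 |
| 24 (one group) | 4.8, so 4 | 6 | 5, 6 |

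**How often the verdicts would differ.** Let X be the number of losses, binomial(n, p) with independent dropout. The documents give only p = 0.20; the other rates are assumed, to show the range.

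| True attrition p | P(10 ≤ X ≤ 12), n = 48 | P(5 ≤ X ≤ 6), one group of 24 |
|---|---|---|
| 10% | 0.018 | 0.078 |
| 15% | 0.152 | 0.229 |
| 20% | 0.352 | 0.351 |
| 25% | 0.372 | 0.361 |
| 30% | 0.223 | 0.278 |

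The last column is for a single group. If the rule had to hold in both groups, the two limits would give different verdicts with probability P(X ≤ 6)² − P(X ≤ 4)², which is 0.15, 0.38, 0.45, 0.31 and 0.14 at the same five rates.

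**Chance of meeting the attrition part** at p = 0.20, n = 48: P(X ≤ 9) = 0.500 and P(X ≤ 12) = 0.852; the difference, 0.352, is the entry in the table. These two figures are upper bounds on the chance of declaring feasibility, because attendance must also pass.

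**Against the completer target.** 48 − 9 = 39 completers under 20%, and 48 − 12 = 36 under 25%. The target of 40 allows 48 − 40 = 8 losses, or 8 / 48 = 16.7%.

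**The case against.** Nobody reading the two statements can make them agree; the case on the other side is about weight.

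- **Feasibility is secondary, and no go/no-go decision is tied to the rule.** The purpose given is to generate data for a full trial, feasibility is also explored in interviews, and the attrition percentage can be reported whatever label it carries. This stands, and it limits the consequence. It does not remove it, because this rule is the plan's only quantitative test of feasibility.
- **The denominator and time point are partly implied elsewhere.** Procedure ties its 20% to families recruited per group and completing the study; Power analysis ties it to 48 recruited and post-treatment data. That helps, but those sentences describe planning, point to different denominators, and do not settle the time point. This is a clarification to make alongside the main correction, not part of the contradiction.
- **The probabilities are softer than their decimals.** Treatment includes group sessions and recruitment is in three cohorts of 16, so dropout may cluster. This is fair. The result that needs no model is that the verdicts differ at 10, 11 or 12 losses of 48.
- **A planning rate and a tolerance limit need not be equal.** This is correct. Agreement with the planning rate makes 20% a reasonable default but does not prove it was the limit intended.
- **The 39-against-40 point is a separate matter,** arising from how 40 was inflated to 48. Agreed; it is worth noting when the limit is chosen, but it is not part of the conflict.

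**Conclusion.** The concern holds. The plan gives two incompatible attrition limits for one decision rule, and the conflict covers 10, 11 and 12 losses of 48 (20.8% to 25.0%), assuming all randomised families are the denominator and attendance is met. With independent dropout, the chance of landing there is 0.35 at the plan's 20% rate and runs from 0.02 to 0.37 across assumed true rates of 10% to 30%. It is therefore most likely to matter close to the attrition the sponsor expects. The effect is confined to the Hypothesis 1 feasibility conclusion; estimates for the primary outcomes are not biased by it. It should be fixed, because feasibility is the first hypothesis of a study that describes itself as a feasibility study and the correction is trivial.

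**What to change.** Before data are seen, state one attrition limit in the same words in the Hypothesis 1 text and in Table 3. For example: attrition of no more than [X]% of all randomised families (n = 48), where a family counts as lost if it has no outcome data at [weeks 15-16 or weeks 32-33].

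The choice of X belongs to the sponsor, since the documents do not settle which limit was intended. 20% is the natural default because it agrees with the analysis text and with the planning rate. In choosing, the sponsor should note that 20% of 48 permits 9 losses and so 39 completers, one short of the stated target of 40; a limit consistent with that target would allow at most 8 losses (16.7%).

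The cost is a one-line correction in two places. Keeping 20% makes the bar stricter than Table 3 now reads, with 9 losses allowed rather than 12.
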